17.0 Potential Benefits to Subjects

17.1 N/A – no benefit.

17.2 Participants may experience no direct benefit.

18.0 Investigator Assessment of Risk/Benefits Ratio: (IRB makes the final determination) *Based upon your response in Sections 17.0 and 18.0, please provide your assessment of risk and benefits in below table.*

Select as applicable:	Pediatric Risk Category:	
x	Category 1	Research not involving greater than minimal risk (45 CFR §46.404 and 21 CFR §50.51)
	Category 2	Research involving greater than minimal risk but presenting the prospect of direct benefit to the individual subjects. (45 CFR §46.405 and 21 CFR §50.52)
	Category 3	Research involving greater than minimal risk and no prospect of direct benefit to individual subjects, but likely to yield generalizable knowledge about the subject's disorder or condition. (45 CFR §46.406 and 21 CFR §50.53)
	Category 4	Research not otherwise approvable which presents an opportunity to understand, prevent, or alleviate a serious problem affecting the health or welfare of children. (45 CFR §46.407 and 21 CFR §50.54)
Select if applicable:	Adult Risk Category:	
x	Not Greater than Minimal Risk	
	Greater than Minimal Risk	

19.0 Data Management and Confidentiality

19.1 **Statistical Analysis Plan.** To address Aim 1, we will compare groups (active vs. sedentary, normal weight vs. overweight/obese) using mixed models (linear or generalized, as appropriate) that adjust

SHORT TITLE:

for clustering of time points within person. For VAS appetite measures, which are assessed at multiple time points within a single measurement session, we will conduct analyses in two ways. First, we will conduct between group analyses using each of the seven individual assessments (e.g. 60 min post-meal) to see if the values differ by physical activity or body weight group. Second, we will also calculate area under the curve (AUC) for each variable of interest (e.g. hunger, ghrelin), and test for group differences on that measure using a linear or generalized regression model. To address Aim 1, hypothesis 2, we will repeat the analyses described above and include insulin sensitivity as a covariate.

- 19.2 The sample size was determined by a review of similar studies indicating a range of 12-44 participants.
- 19.3 All study staff will complete research training, save study documents on drives that require authorization of access, password protection, or encryption. Paper study documents will be protected using physical controls (such as being kept in secured locked offices in locked file cabinets). Study staff will keep identifiers separate from study IDs and data [master list]) during storage, use, and transmission.
- 19.4 A Certificate of Confidentiality has been issued for this study. Certificates are automatically issued for NIH funded research per [NIH policy](#).
- 19.5 Study surveys will use a study ID for an identifier, study staff will lock documents in secure office locations and keep data collection surveys and instruments with them at all times when in use.
- 19.6 Describe how data or specimens will be handled study-wide:
 - Study ID and visit date will be included on source documentation
 - Study documents will be stored in secure offices in secure file cabinets, Redcap, the W drive, or BOX (the study team has previous approval to use).
 - Study source documentation and other data will be kept at least 3 years after submission of the Final Progress Report to the NIH.
 - The CMH study team, other approved staff members from approved organizations (KUMC, etc), the sponsor (NIH), the IRB.
 - The study lab coordinator, the PI.
 - No data will need to be transported, but blood samples will be transported to the analyzing lab through standard biohazard

shipping protocols. All data obtained off of CM premises will be accessed by study staff electronically via approved secure sharing platforms such as OneDrive.

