6.0 Procedures Involved

- 6.1 This is a cross-sectional study design (see above figure). The study team aims to assign N=10 participants to each arm of the study (normal weight/active, normal weight/sedentary, overweight, obese/active, and overweight, obese/sedentary).
- 6.2 Participants who fall into the overweight/obese category (~20) will also be recruited for the AAAA2 – Exercise study (AAAA2 study with an intervention and post intervention tests), which includes the same testing as AAAA2. The AAAA2 - Exercise study will only include those with a BMI percentile from the 85th to 99th percentile. It also has an exercise intervention (same as the BATE study), which 50% of study participants will be randomly assigned to. All 3 visits (measurement session 1, measurement session 2 and insulin sensitivity visit) will be completed before and after the exercise intervention. For those participants that complete testing in the AAAA2 study and are interested in the AAAA2 – Exercise study, their AAAA2 data will be used as baseline data in the AAAA2 - Exercise study. They will then consent for the AAAA2 - Exercise study and start their exercise intervention, or wait until their follow-up visits.

Orientation Session: 1 hour. The orientation session will serve as a visit to explain the details of the study, with example images of what tests will be completed. P/A/C documentation will also be completed at this visit if they decide to participate. If a participant and parent opt for in-person orientation, after consent, their height, weight and blood pressure will be collected to classify each participant into an arm of the study. If a virtual orientation is chosen, height and weight will be reported from them, according to their most recent measures. Following P/A/C for both in-person and virtual orientation, the **Contact Information Questionnaire** will be completed. After completion of the orientation session, the parent and subject will be instructed to complete the **Medical History and Demographics Questionnaire** prior to the first measurement session visit. This questionnaire will be sent through a RedCap link.

Measurement Session 1: 5.0-6.0 hours. This study visit will take place at the Don Chisholm Center in the morning (<9:00am) following an overnight dietary fast. This study visit will be conducted to assess appetite control and relevant variables under laboratory conditions. The measures conducted in this visit are provided below

- **Surveys**

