11.0 Inclusion and Exclusion Criteria

11.1

Inclusion Criteria

- Males (~50%) and females (~50%)
- Age 14-17 (Tanner Stage III-V, as determined via self-assessment)
- Non-smoking
- Not currently involved in any other research study

- Willing to give informed consent to participate

Exclusion Criteria

- Age <14 or >18 at time of enrollment
- Restrained eater (>13 on the restraint section of the three-factor eating questionnaire; Current/past diagnosis of an eating disorder).
- Self-reported medical conditions (including, but not limited to, diabetes, Crohn's disease, etc.) that may affect adherence to the protocol, exercising safely, or alter metabolism
- Taking medications known to affect metabolism (e.g. thyroid medication, β -blockers, or stimulants).
- Gave birth in the past 12 months or <6 months post-lactation.

Individuals who are not yet adults (infants, children, teenagers) will be included in this study (teenagers age 14-17).

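### Section 19.1 compares observed active and sedentary groups without sex or age in the model, which leaves the activity contrast open to confounding of unknown and possibly small size

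*Combined protocol and SAP*

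**What the plan says.** The main comparison in section 19.1 reads "we will compare groups (active vs. sedentary, normal weight vs. overweight/obese) using mixed models (linear or generalized, as appropriate) that adjust" and continues after a page break "for clustering of time points within person". Individual time points are examined "to see if the values differ by physical activity or body weight group". The AUC regression names no covariates. For Hypothesis 2, "we will repeat the analyses described above and include insulin sensitivity as a covariate"; that is the only covariate named anywhere in the plan.

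The study is cross-sectional. At an in-person orientation (section 6.2), "their height, weight and blood pressure will be collected to classify each participant into an arm of the study". Random assignment is mentioned only for the separate exercise study.

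Eligibility (section 11.1) is "Age 14-17 (Tanner Stage III-V, as determined via self-assessment", with roughly equal numbers of males and females overall. The readable text states no balance or matching by activity group; the design figure is not shown. Section 12.1 aims for four cohorts of 10, 40 in all.

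Section 3.1 places the start of the decline in activity at about 15 years in boys and 10-13 years in girls. Hypothesis 1 (section 2.2) expects an activity difference in appetite irrespective of weight status. Section 3.3 expects to describe what activity and obesity each contribute independently.

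**The concern.** Participants fall into the active or sedentary group by their own behaviour. The protocol's background links that behaviour to sex and age, and the stated ages of decline overlap or precede the 14-17 entry range. The active and sedentary groups may therefore differ in sex mix and mean age. If sex or age also affects an appetite outcome, the unadjusted activity contrast absorbs part of that effect. A difference due to sex or age could then be reported as altered appetite control, or could hide a real difference.

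Outcomes need not be equally exposed. The fixed breakfast is sized at 40% of RMR (section 6.2, Measurement Session 1), which may lessen body-size differences in the hunger and hormone responses that follow it. The ad libitum meal is not scaled, so its kcal outcome may be the most exposed.

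**Working it through.** **The plan's own figure.** 4 cohorts x 10 = 40, as stated. Section 19.2 rests the sample size on a range of 12-44 in similar studies and gives no alpha, power, SD or effect size. Everything below is in SD units and assumes two-sided 5%, 80% power, one summary value per participant (AUC, kcal or a single time point), residual SD 1 and no true activity effect.

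**Models.** A = activity + weight group (residual df 40 - 3 = 37). B = A + sex + age (df 40 - 5 = 35).

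**Bias formula.** For sex, bias in A = (difference in male share between activity groups) x (sex effect). For age, bias = (gap in mean age) x (slope per year).

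**Sex only.** Sex is drawn at random within each activity group with the stated male shares, active vs. sedentary; 20,000 simulated trials. Shares and sex effects are assumptions.

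| Male share | Sex effect | Share difference x effect | Simulated bias, A | Type I error, A |
|---|---|---|---|---|
| 55/45 | 0.3 | 0.10 x 0.3 = 0.03 | 0.033 | 5.2% |
| 60/40 | 0.3 | 0.20 x 0.3 = 0.06 | 0.065 | 5.3% |
| 60/40 | 0.6 | 0.20 x 0.6 = 0.12 | 0.126 | 6.7% |
| 60/40 | 1.0 | 0.20 x 1.0 = 0.20 | 0.195 | 8.4% |
| 70/30 | 0.3 | 0.40 x 0.3 = 0.12 | 0.118 | 6.7% |
| 70/30 | 0.6 | 0.40 x 0.6 = 0.24 | 0.238 | 10.9% |
| 70/30 | 1.0 | 0.40 x 1.0 = 0.40 | 0.395 | 19.4% |

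Repeat runs agreed within simulation error (up to 20.6% in the last row). These rates describe groups drawn from populations with those shares. If the sample split is exactly 12/8 males, type I error is lower, 5.6-5.9% for a sex effect of 0.6-1.0 SD.

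**Age only** (10,000 simulated trials; slopes of 0.1, 0.2 and 0.3 SD per year assumed).

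- Gap of 0.25 year: bias 0.025, 0.048, 0.081; type I error 5.3%, 5.5%, 5.7%.
- Gap of 0.5 year: bias 0.049, 0.098, 0.151; type I error 5.1%, 6.2%, 7.2%.
- Gap of 1 year: bias 0.097, 0.196, 0.308; type I error 6.1%, 8.8%, 15.0%.

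Model B had bias of at most 0.008 SD and type I error near 5% throughout. That holds by construction, because only sex and age were simulated as confounders.

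**Price of adjustment.** Root mean square error (RMSE) = sqrt(bias^2 + SE^2), with bias in B taken as zero.

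| Setting | RMSE of A | RMSE of B |
|---|---|---|
| 55/45, 0.3 | sqrt(0.033^2 + 0.317^2) = 0.319 | 0.325 |
| 60/40, 0.3 | sqrt(0.065^2 + 0.318^2) = 0.325 | 0.331 |
| 60/40, 0.6 | sqrt(0.126^2 + 0.327^2) = 0.350 | 0.331 |
| 60/40, 1.0 | sqrt(0.195^2 + 0.350^2) = 0.401 | 0.331 |
| 70/30, 0.3 | sqrt(0.118^2 + 0.317^2) = 0.338 | 0.357 |
| 70/30, 0.6 | sqrt(0.238^2 + 0.326^2) = 0.404 | 0.357 |
| 70/30, 1.0 | sqrt(0.395^2 + 0.346^2) = 0.525 | 0.357 |

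A does slightly better in the three settings with a 0.3 SD sex effect (by 0.006 to 0.019 SD). B does better in the other four (by 0.019 to 0.168 SD).

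**Detectable difference with no sex effect** (noncentral t). A: SE sqrt(2/20) = 0.316, df 37, gives 0.91 SD. B: SE 0.3255, 0.3335 and 0.360 at 50/50, 60/40 and 70/30, df 35, gives 0.94, 0.96 and 1.04 SD.

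**The case against.** **Half of the confounding argument is not in the documents.** Section 3.1 links sex and age to activity; nothing states a sex or age effect on appetite. Section 3.2 gives fat-free mass and resting metabolic rate a role in appetite control, which makes a sex effect plausible, but that is inference. This stands. A reader might infer that the contrast is shown to be biased, or that the error rate is near 20%. The documents support neither: the upper end needs about 70/30 and a 1.0 SD sex effect, both assumed.

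**Small samples are often unbalanced by chance.** A reader might take likely chance imbalance in a sample of 40 as further evidence. It is not. If sex is unrelated to activity, the unadjusted contrast has no bias and type I error stays at about 5%, because chance imbalance is already in the standard error. Only systematic imbalance counts.

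**Entry limits and the missing figure.** The narrow age range, the Tanner limits and the overall sex target reduce the scope for imbalance. The absence of balance by group can be asserted only for the readable text.

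**Adjustment is not always better.** This is correct for a sex effect of about 0.3 SD, though the loss is small.

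**Weight status.** A reader might infer that Hypothesis 1 requires an interaction test. It does not: an activity effect adjusted for weight group satisfies its wording. At 10 per cohort the interaction could settle little anyway. What remains is that section 19.1 does not say activity and weight group enter one model.

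**Modest aims.** The objective is an association, and the stated primary endpoint is enrolment. This supports a low severity, although section 3.3 does intend to separate the contributions of activity and obesity.

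**Conclusion.** The point holds as a minor one. As written, section 19.1 leaves the activity contrast unprotected against two variables that the protocol itself ties to activity. The size is unknown and may differ by outcome. Systematic sex imbalance of 55/45 to 60/40 with a 0.3 SD effect is negligible. At 60/40 with 0.6-1.0 SD the effect is modest. Only about 70/30 with 0.6-1.0 SD, or a mean-age gap near one year with a slope of 0.2-0.3 SD per year (bias 0.20-0.31 SD, type I error 9-15%), is material. All shares, effects, gaps and slopes are assumptions.

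The case for acting does not rest on demonstrated bias. The remedy is cheap, and naming the covariates now removes a later choice among models across many outcomes and time points. Adjusting for sex and age would still not establish an independent effect of activity, since other confounding remains.

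**What to change.** In section 19.1, specify as the main analysis for each Hypothesis 1 outcome one joint model with activity, weight group, sex and age, plus time point for repeated outcomes. Carry sex and age into the Hypothesis 2 model that adds insulin sensitivity. State that confounding by other factors remains possible.

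Optionally, as an estimation-only secondary analysis, report the activity effect within each weight group and the interaction, with 95% confidence intervals. State that a non-significant interaction will not be read as the same effect in both groups. With 10 per cohort and sex and age in the model, half-widths are about 0.93-0.98 SD within a weight group and about 1.3 SD for the interaction.

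**Cost.** SAP wording only. Age is an entry criterion, sex is a recruitment target, and the "Medical History and Demographics Questionnaire" is already planned. The model uses two more degrees of freedom (37 to 35; 36 to 34 for Hypothesis 2). The detectable difference rises from 0.91 SD to 0.94-0.96 SD, or 1.04 SD at 70/30. If the sex effect is only about 0.3 SD, RMSE is worse by about 0.006-0.02 SD. A large age gap between the activity groups would also cost some precision.

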3.3 **New Approaches.** The proposed research is innovative because it shifts beyond the tonic inhibition approach, to include the regulation of appetite via energy expenditure and metabolic function. Our preliminary studies (see sections 2.1-2.5) indicate that energy intake and disinhibition become dysregulated at low levels of physical activity, resulting in 3.8 fold greater fat mass 1 year later [50]. We will extend previous findings in adults to adolescents, a previously unexamined population in regard to this concept. Additionally, we have expanded upon previous studies in the proposed project by exploring plausible metabolic mechanisms that underlie appetite dysregulation at low levels of activity. By completing this work, it is our expectation that we will have described the independent effects of physical activity and obesity on appetite and energy metabolism in adolescents.

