 - **TFEQ**
 - **CEQ**
 - **VAS Pre-Meal**
 - **VAS Post-Hedonic**
 - **VAS**
- **Anthropometry and Body Composition via DXA.**
 - Fat mass (FM) and fat-free mass (FFM) will be measured using a whole-body dual energy X-ray absorptiometer (DXA, Lunar DPX system, version 3.6).
- **Waist and Hip Measurements.** Waist measured in centimeters, two inches above the umbilicus at skin level, at the end of a normal breath expiration, with arms relaxed at sides. Hip measured in centimeters at the maximum circumference of the buttocks, with arms relaxed at the sides.

- **Fixed/*Ad libitum* Meals.** Appetite (see below) will be assessed following a fixed standard breakfast (40% of RMR, composed of 55% carbohydrate, 15% protein, 30% fat). Food intake (total kcals) will also be assessed using an *ad libitum* meal served three hours after the fixed meal. Participants will be instructed to eat until comfortably full and informed that they can request more of the meal at any point.
- Each plate of food will be weighed before and after serving, without the subjects' knowledge.
- **Appetite and Eating Behavior** Subjective assessment of hunger and palatability will be completed using self-rated visual analogue scales (VAS) [51], with each scale consisting of a 10-cm long line separating statements such as "not at all hungry" and "extremely hungry". [VAS tools are widely used to assess health conditions and show good test-retest reliability [52], especially in within-subject repeated measures study designs [53].] Perceptions of dietary restraint, disinhibition, and hunger will be measured during each measurement session using the Three Factor Eating Questionnaire (TFEQ) [54]. The Control of Eating Questionnaire (CEQ) will be used to assess hunger, fullness, cravings, the desire to eat certain types of foods, and the ability to resist urges to eat [55]. Objective assessment of appetite will be completed using blood samples taken from an indwelling catheter, and analyzed for episodic regulation of the following fasting and satiety hormones: glucose, insulin, leptin, ghrelin, glucagon-like peptide 1 (GLP-1), and peptide YY (PYY). All samples will be mixed a standard preservative (400 μ L of 10,000 KIU aprotinin), centrifuged, the plasma divided and stored in -80°C freezer until later analysis.

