- **Resting Metabolic Rate.** Resting metabolic rate (RMR) will be measured via indirect calorimetry using a ventilated hood and open-circuit system metabolic cart (ParvoMedics, Salt Lake City, Utah) following a standard protocol [56].
- Thermic effect of feeding (TEF) will measure the energy expenditure resulting from digestion following the fixed meal using the ventilated hood.

Continuous, Free-living Home Assessments of Energy intake/expenditure: 7 days between Measurement Session 1 and Measurement Session 2.

- The free-living assessment period is defined as the 7 days between Measurement Session 1 and Measurement Session 2. During these 7 days, subjects will be completing two energy intake/ expenditure assessments while going about everyday life activities at home. These assessments are explained in proceeding bullets.
- Energy intake will be assessed during the free-living 7-day assessment period via standardized 24-hour dietary recalls. Energy intake will be assessed using three dietary recalls occurring on randomly selected non-consecutive days over each 7-day free-living assessment period

(including at least one weekend day) to minimize preparation that could bias recall, by a team of experienced staff employing a multi-pass approach, which utilizes prompts to reduce food omissions and standardizes the interview methodology.

- Physical activity and energy expenditure will be estimated using two physical activity monitors (Actigraph GT9X Link, Actigraph Inc., and ActivPAL, PAL Technologies), which assesses movement using tri-axial accelerometry. The monitors themselves are not being studied as a part of this protocol, and while they do not have 501(k) documents, the devices used in this study are not considered to be more than minimal risk.

Measurement Session 2: 2.0 hours. This study visit will take place at the Don Chisholm Center. This visit will include a DXA scan, mitochondrial function testing via NIRS, and cardiorespiratory fitness testing (CRF):

- **Body Composition via DXA:**
 - Fat mass (FM) and fat-free mass (FFM) will be measured using a whole-body dual energy X-ray absorptiometer (iDXA, Lunar DPX system) with the participant dressed in surgical scrubs and in bare feet.
- **Grip Strength Testing:**
 - Grip strength will be assessed using a handheld dynamometer. The participant will hold the device in one hand in line with the forearm at the level of the thigh, away from the body.

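### Section 19.1 controls body weight only by a two-level class, so its activity contrast does not by itself support the claim in Section 3.3 of effects independent of obesity

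*Combined protocol and SAP*

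**What the plan says.** Section 19.1 sets out the analysis in group terms: "we will compare groups (active vs. sedentary, normal weight vs. overweight/obese) using mixed models (linear or generalized, as appropriate"). The analyses at individual VAS time points look "to see if the values differ by physical activity or body weight group". The AUC analyses "test for group differences on that measure using a linear or generalized regression model". For Hypothesis 2 the same analyses are repeated to "include insulin sensitivity as a covariate". That is the only covariate named, and no model contains fat mass, percent fat, fat-free mass or continuous BMI.

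Body composition is nevertheless measured. At Measurement Session 1, the appetite visit, Section 6.0 states: "Fat mass (FM) and fat-free mass (FFM) will be measured using a whole-body dual energy X-ray absorptiometer". For Measurement Session 2 it adds: "This visit will include a DXA scan, mitochondrial function testing via NIRS, and cardiorespiratory fitness testing (CRF").

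Two claims rest on these models. Hypothesis 1 (Section 2.2) expects appetite to differ between sedentary and active adolescents whatever their weight status. Section 3.3 goes further and expects that "we will have described the independent effects of physical activity and obesity on appetite and energy metabolism in adolescents".

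Arms are assigned from height and weight at orientation, as reported by the family if orientation is virtual (Section 6.0). Section 11.1 gives no BMI limits for this study. The limit that does appear belongs to the linked study: "The AAAA2 - Exercise study will only include those with a BMI percentile from the 85th to 99th percentile".

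**The concern.** Activity is observed here, not assigned. Filling four arms with 10 each makes activity and weight class orthogonal, so differences between classes cannot confound the activity contrast. Nothing in the design matches active and sedentary participants on adiposity inside a class. The upper class may be wide, since no ceiling is stated for this study.

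The protocol's own background links adiposity to both sides of the comparison. Section 3.2 reports that the least active adults gained the most fat, cites observational data tying obesity to poorer appetite regulation, and describes leptin as a signal of energy storage. Leptin is also a Hypothesis 1 outcome. If the sedentary members of a class are fatter than the active members, the class-only contrast carries part of that difference. A reader of Section 3.3 would then take it as an activity effect separate from obesity.

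**Working it through.** **Inputs from the documents.** Four arms of 10 (Sections 4.1 and 12.1), so 4 × 10 = 40, or 20 active versus 20 sedentary. Background share overweight or obese: 31.8% (Section 3.1). Section 19.2 bases the sample size on similar studies and gives no alpha, power, effect size or SD, so the plan has no figure to reproduce on this point.

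**Assumed inputs.** Outcome SD of 1; two-sided alpha of 0.05; no direct effect of activity; activity and class entered together. The within-class fat gap, in SD of fat mass, and the outcome slope per SD of fat mass are varied.

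**Formulas.**
- Spurious contrast = gap × slope.
- SE of a 20 versus 20 contrast = √(2/20) = 0.316.
- Shift = contrast / 0.316.
- Rejection = Φ(shift − 1.96) + Φ(−shift − 1.96).

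| Gap (SD) | Slope | Contrast (SD) | Shift | Rejection |
|---|---|---|---|---|
| 0.25 | 0.2 | 0.05 | 0.16 | 5.3% |
| 0.50 | 0.3 | 0.15 | 0.47 | 7.6% |
| 0.60 | 0.4 | 0.24 | 0.76 | 11.8% |
| 0.75 | 0.5 | 0.375 | 1.19 | 22.0% |
| 1.00 | 0.4 | 0.40 | 1.26 | 24.4% |
| 1.00 | 0.5 | 0.50 | 1.58 | 35.3% |

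**Simulation of the quota design.** Participants were drawn 10 per cell from a population with the weight class cut at 31.8% and activity split at its median. Assumed ranges were an activity-fat correlation of −0.2 to −0.6, a BMI-fat correlation of 0.70 to 0.85 and a slope of 0.3 to 0.5, with 2,000 replicates per setting.
- The fat gap within a class was 0.15 to 0.74 SD despite the quota.
- Class-only model: spurious contrast 0.05 to 0.35 SD, rejection 5.1% to 22.2%.
- With continuous fat mass added: mean effect within 0.01 SD of zero, rejection 4.0% to 5.5%. Monte Carlo error near 5% is √(0.05 × 0.95 / 2000) = 0.5 percentage points.
- SE of the activity effect: 0.29-0.31 without fat mass, 0.28-0.34 with it.

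**Setting the within-class correlation directly.** With equal numbers active and sedentary, a within-class correlation r corresponds to a gap of 2r within-class SDs: 0.6, 0.8 and 1.0 for r = 0.3, 0.4 and 0.5. At slope 0.4 the formula gives 0.24, 0.32 and 0.40 SD. Simulation (2,500 and 4,000 replicates) gave 0.24-0.25, 0.31 and 0.39-0.40 SD, with rejection of 11-12%, 16% and 22-24%. At r = 0.1 rejection was 5-6%. Adding fat mass again gave about zero and about 5%.

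**Scale.** With 20 versus 20, the difference detectable with 80% power is (1.96 + 0.84) × 0.316 = 0.89 SD. A spurious contrast of 0.4 SD is a little under half of that.

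**The case against.** Four points can be made for the plan as written.

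- Hypothesis 1 speaks of weight status, which is naturally a category, and the design crosses activity with that category in equal numbers. This stands. The class-only contrast answers the class-level question.
- Calling the contrast spurious presumes that fat mass confounds activity. Section 3.2 puts fat gain downstream of low activity and of dysregulated appetite. Fat mass may then be partly a mediator, or a result of appetite itself, and conditioning on it could remove part of the association of interest. This stands too, and it argues against replacing the class-only model with the adjusted one.
- Every strength of association above is assumed, and the weak end is harmless. This stands, so the range has to start at about 5%.
- The protocol's rationale stresses fat-free mass. The title of reference 16 ties self-determined meal size to fat-free mass and not to fat mass or BMI, so a fat-mass slope of 0.4 is doubtful for ad libitum intake. This stands for that outcome. It is weaker for leptin, which the protocol itself treats as a signal of stored energy.

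A reader might infer that the activity conclusion fails even if every step is carried out as written. The documents do not support that for the class-level reading of Hypothesis 1. A reader might also infer that the overweight/obese arms are defined from the 85th percentile upward. That cut-off appears only in the background and in the description of the linked study.

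**Conclusion.** The point holds in a limited form. The plan has no term for adiposity within a weight class, although it collects the data for one. The class-only contrast can support a statement about activity across weight classes. It cannot alone support the stronger statement in Section 3.3.

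If fat mass drives the outcome and activity has no direct effect, the spurious contrast ranges from about 0.05 SD, which is negligible, to about 0.4 SD, with rejection of about 22-24% against a nominal 5%. This covers slopes of 0.3 to 0.5 in the quota simulation and 0.4 where the within-class correlation was set directly. More extreme inputs go higher, such as 35% at a gap of 1.0 SD and a slope of 0.5. Nothing in the documents shows where this study lies in the range, and the figures do not apply if fat mass is wholly a consequence of inactivity or of appetite. They show what could happen, not that the results will be biased.

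**What to change.** In Section 19.1, keep the class-only model. For each Hypothesis 1 outcome, prespecify beside it the same model plus one continuous DXA fat measure, named in advance (for example fat mass index) and taken from a named scan. The Session 1 scan is the natural choice because it belongs to the appetite visit. For ad libitum intake, include fat-free mass as well. Report both models for every outcome. Tie the wording of Section 3.3 to them: claim an activity effect independent of adiposity only if it holds in the adjusted model, and otherwise describe a difference across weight classes.

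The cost is SAP text, one degree of freedom (two for ad libitum intake) and a slightly larger standard error in some settings: from about 0.31 to at most 0.34 SD in the quota simulation, and up to 0.355 SD in the least favourable setting of the other. No new data are needed. Because fat mass may partly follow from low activity or from appetite, the SAP should say that the adjusted estimate is the association not explained by adiposity and is not a total effect. Naming the covariates now also prevents the adjustment from being chosen after the results are seen.
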